### 9.2.3 Common Variable Derivations

Variable	Data Type	Definition/Calculation	Note
Change from Baseline	All	Post-dose Observation minus Baseline Observation	
Analysis Period	All	Time period starting 1 day before dosing of each of the treatments and ends 1 day before dosing in next analysis period or at the start of the follow-up period for the last treatment.	
Analysis Study Day (Prior to first Dose)	All	Date of Measurement minus Dose Date	
Analysis Study Day (Post first Dose)	All	Date of Measurement minus Dose Date +1	

### 9.2.4 QC

The analysis datasets and the TFLs will be QC'd according to the general PRA EDS QC plan.

#### 9.2.4.1 Critical Data

The QC plan requires datasets be classified as critical or non-critical. As the primary objective of this study is to characterize the PK the datasets considered critical are subject level and PK (ADSL, ADPC, ADPP). As these are related to the primary objectives these datasets will be double programmed per the QC Plan.

### 9.2.5 ADaM Datasets and Metadata

The analysis datasets will be generated in accordance with Clinical Data Interchange Standard Consortium (CDISC) Analysis Data Model (ADaM) Version 2.1. At least the following datasets will be created:

- ADSL
- ADAE
- Laboratory Analysis Dataset (ADLB)
- Vital Signs Analysis Dataset (ADVS)
- ECG Analysis Dataset (ADEG)
- ADPC
- ADPP

ADaM compliant datasets will be delivered to the Sponsor. A define.xml file Version 2 with the corresponding metadata will be included. Analysis results metadata are excluded.

## 9.3 Software

The statistical analysis and reporting will be done using SAS® for Windows™ Version 9.4 or higher (SAS Institute, Inc.).

PK parameter calculations will primarily be done using Phoenix® WinNonlin® Version 8.1 or higher. Additional PK computations may be performed in SAS®.

---

## 9.4 Statistical Methods

### 9.4.1 Statistical Outlier Determination

No statistical outlier analysis is planned.

### 9.4.2 Predetermined Covariates and Prognostic Factors

CYP3A4 genotype will be investigated as a factor in this study. PK tables will be presented by CYP3A4 genotype.

The pharmacogenetics of other isoforms, metabolizing enzymes, transferases, transporters, etc, possibly involved in the absorption, distribution, metabolism and excretion of balovaptan and its major metabolites (e.g., CYP3A and P-glycoprotein) may be investigated additionally (e.g. CYP3A5 genotype). Beside CYP3A, transporters that will be investigated (others may follow) are: P-glycoprotein (ABCB1), OCT2 (SLC22A2), OATP2B1 (SLCO2B1), AOT3 (SLC22A8). The results may be pooled with data from other studies of balovaptan and will be reported separately.

### 9.4.3 Hypothesis Testing

No formal hypothesis testing will be done.

## 9.5 TFL Layout

Report layout will be according to the PRA EDS – ICH E3 compliant – CSR Template. The layout of TFLs will be according to the PRA EDS standards.

No table shells will be provided. The TFLs will be provided in Adobe PDF format.

Format:

- Page size: A4
- Data in listings will be sorted by subject number and time point.
- Data in tables will be sorted by treatment and time point.
- Column titles will be in title case letters.
- All tables and listings will be in landscape format.
- The treatment labels will be as outlined in [Section 9.2.2 Treatment/Subject Grouping Definition](#).

## 10.0 Analysis Populations

Analyses	Safety	Pharmacokinetic
Disposition Summaries	✓	
Safety Assessments	✓	
Baseline Characteristics	✓	✓
Primary Analysis		✓
PK Concentrations		✓
PK Parameters		✓

### 10.1 Safety Analysis Population

The safety set will consist of subjects who receive at least one dose of balovaptan. This set will be used for the safety data summaries and baseline characteristic summaries.

### 10.2 Pharmacokinetic Analysis Population

The PK set will consist of all subjects who receive at least 1 dose of balovaptan. Subject will be excluded from the PK set if they significantly violate the inclusion or exclusion criteria, deviate significantly from the protocol, or if data are unavailable or incomplete. Excluded cases will be documented together with the reason for exclusion in the CSR. All decisions on exclusions from the analysis will be made prior to database closure.

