13. Screening or baseline ECGs with QRS and/or T-wave judged to be unfavorable for a consistently accurate QT measurement (i.e., neuromuscular artifact that cannot be readily eliminated, arrhythmias, indistinct QRS onset, low amplitude T-wave, merged T- and U-waves, prominent U-waves, etc.).
14. Screening or baseline ECG with evidence of clinically relevant abnormalities, e.g. atrial fibrillation, atrial flutter, complete bundle branch block, Wolf-Parkinson-White Syndrome, or cardiac pacemaker.
15. Systolic blood pressure greater than 139 or less than 90 mmHg, or diastolic blood pressure greater than 89 or less than 45 mmHg, based on the average of ≥ 3 consecutive measurements.
16. Clinically significant abnormalities in laboratory test results (including hepatic and renal panels, complete blood count, chemistry panel, coagulation parameters, and urinalysis). In the case of uncertain or questionable results, tests performed during screening may be repeated on Day -1 of Period 1 to confirm eligibility.
17. History of coagulopathies, bleeding disorders, or blood dyscrasias.
18. Subjects who have smoked within 3 months prior to first dose administration.
19. Any clinically relevant history or any suspicion of alcohol and/or other substance abuse or addiction. Past alcohol and/or other substance abuse or addiction is also not allowed.
20. Alcohol consumption of >24 units per week for males and females. One unit of alcohol equals $\frac{1}{2}$ pint (285 mL) of beer or lager, 1 glass (125 mL) of wine, or $\frac{1}{6}$ gill (25 mL) of spirits.
21. Positive urine alcohol test or urine drug screen at screening or each admission (Day -1 of each period) (barbiturates, benzodiazepines, methadone, amphetamines [including ecstasy], methamphetamines, opiates, cocaine, and cannabinoids).
22. Positive result on human immunodeficiency virus (HIV)-1, HIV-2 antibodies, hepatitis C virus (HCV) antibody, hepatitis B virus surface antigen (HBsAg), or hepatitis B core (HepBc) antibody screen.
23. Participation in an investigational drug or device study within 90 days prior to first dosing, or within 5 months prior to first dosing in case of a study with a biological, as calculated from the day of follow-up from the previous study.
24. Any donation of blood or plasma or significant blood loss within 3 months prior to screening.

25. Dietary restrictions that would prohibit the consumption of standardized meals.

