5.1.2 Management of Toxicities and of Subjects Who Experience Adverse Events

5.1.2.1 Management Guidelines

In general, any emerging AEs must diligently be watched, treated as medically indicated according to common medical practice and documented in terms of onset-date, intensity, off-set date, and any measures taken to treat the AE.

No specific treatment guidance to any potentially emerging AEs in balovaptan clinical trials exist and treatment should be according to the common medical practice for the given AE.

The Investigator should also consider discontinuation of treatment with balovaptan, in particular in case an AE is of severe intensity and considered to be possibly related to balovaptan.

Temporary dosing interruptions must be discussed with the Sponsor's Medical Monitor in the sense that temporary interruptions will have to be very limited in order to not jeopardize the trial's PK objectives. Dose modifications because of an AE are not allowed in this study.

[REDACTED]

[REDACTED]

[REDACTED]

[REDACTED]

- [REDACTED]

[REDACTED]

[REDACTED]

[REDACTED]

[Redacted text block]

[Redacted text block]

[Redacted text block]

[Redacted text block]

[Redacted text block]

[Redacted text block]

[Redacted text block]

- [Redacted list item]
- [Redacted list item]

[Redacted text block]

[REDACTED]

[REDACTED]

[REDACTED]

[REDACTED]

[REDACTED]

[REDACTED]

[REDACTED]

[REDACTED]

[REDACTED]

[REDACTED]

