### 3.0 Introduction

This Statistical Analysis Plan (SAP) describes the statistical methods that will be used during the analysis and reporting of data collected under F. Hoffmann-La Roche Ltd Protocol WP40607.

This SAP should be read in conjunction with the study protocol and electronic case report form (eCRF). This version of the plan has been developed using the protocol dated 22-Oct-2018 (including all amendments up to this protocol date) and the final eCRF(s) dated 08-Jan-2019.

An approved and signed SAP is a requirement for database lock.

This SAP only covers the results that will be processed by the PRA Early Development Services (EDS) Biostatistics Department.

PRA EDS will perform the pharmacokinetic (PK) and safety and tolerability evaluation.

This SAP supersedes the statistical considerations identified in the protocol; where considerations are substantially different, they will be so identified. Any post-hoc or unplanned analyses, or significant changes from the planned analysis in this SAP performed to provide results for inclusion in the clinical study report (CSR) but not included in this SAP, will be clearly identified in [Section 9.8.2](#) of the CSR. Changes to planned analyses do not require an updated SAP but should be included in the CSR if significant.

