## 6.1 Sample Size Considerations

This is an exploratory study for which no formal statistical hypothesis will be tested, and therefore the sample size is chosen to estimate the absolute bioavailability of the 10 mg single dose with sufficient precision. A total of 8 subjects per cohort are to be enrolled with the target of at least 6 subjects available for the primary PK analysis (i.e., having taken a single dose of 10 mg on Day 1 and completed all PK assessment up to Day 10). If the number of subjects providing PK data from the multiple dose parts of the study is lower than 6 for either cohort more subjects may be enrolled.

Assuming a within-subject variability of around 35% it can be estimated that with 6 subjects the half-width of the 90% confidence interval (CI) for the ratio of geometric means of the microdose IV kinetics with that from the oral dose (i.e. CL versus CL/F) would be obtained by dividing/multiplying the ratio estimate by a factor of 1.50. The within-subject variability value of around 35% has been identified as a reasonable assumption: it is smaller than the observed 42% between-subject variability for the apparent clearance of distribution (CL/F) from a single oral 10 mg dose in study WP40038, and it considers that the reference will be obtained from IV kinetics, which is expected to be less variable than oral kinetics.

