### 16.2.2 Pharmacokinetic Parameters

Plasma PK parameters for balovaptan, [C]-balovaptan, M2 and M3, will be estimated using non-compartmental methods with WinNonlin®.

The plasma PK parameters will be estimated from the concentration-time profiles. In estimating the PK parameters, BQL values will be set to zero for the pre-dose PK sample, as well as for all other samples being BLQ and occurring before  $t_{max}$ . For subsequent time points, the result will be set to missing. Actual sampling times, rather than scheduled sampling times, will be used in all computations involving sampling times. If the actual time or dose time is missing, the scheduled time may be substituted in order to calculate the PK parameter.

Descriptive statistics (number of subjects, arithmetic mean, geometric mean, SD, geometric and arithmetic CV, median, min, and max) will be used to summarize the calculated PK parameters by treatment, day and analyte. For  $t_{max}$ , only median, min and max will be presented.

The points to be included in the  $\lambda z$  range will be determined by the pharmacokineticist after inspection of the semi-log concentration-time profiles. At least 3 points will be required to be used and the range should ideally be spread over a time interval representing at least 2 half-lives. The  $C_{max}$  data point will not be included.

Parameters based on  $R^2$  below 0.70 or %AUCextra above 20% will be flagged and excluded from descriptive statistics.

The ratio of geometric means from the microdose IV kinetics with that from the oral dose will be estimated using an analysis of variance (ANOVA) of the natural logarithm transformed clearance (CL and CL/F). A mixed model will be used, separately for the 2 cohorts with the 2 doses of 10mg and 50mg, and will include fixed effects for route (oral or iv) and for day (1 and 14) and a random effect for subject. From this model the least-squares means (LSMeans) for clearance (CL) of [C]-balovaptan iv and for CL/F of oral balovaptan will be presented. The ratios of the LSMeans for the comparison of CL to CL/F (IV/Oral) will be obtained by exponentiating the difference of the LSMeans on the log scale. A 90% confidence interval for the ratios of the treatment means will be calculated.

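### Could the by-subject exclusion rule in SAP 10.2 cost the primary analysis valid single-dose data because of a Period 2 event?

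*SAP*

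**What the plan says.** SAP 10.0 tabulates two populations, Safety and Pharmacokinetic. The row "Primary Analysis" falls under the Pharmacokinetic set, as do PK concentrations and PK parameters.

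SAP 10.2 admits anyone who received at least one dose and then sets three grounds for removal. Two concern eligibility and conduct: "Subject will be excluded from the PK set if they significantly violate the inclusion or exclusion criteria, deviate significantly from the protocol". The third concerns the measurements themselves: "or if data are unavailable or incomplete". Protocol 6.6 has the same rule. Both require the decisions before database closure and the reasons documented.

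SAP 6.1 and protocol 6.1 describe who is available for the primary PK analysis in Period 1 terms only: "having taken a single dose of 10 mg on Day 1 and completed all PK assessment up to Day 10".

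The model in SAP 16.2.2 is fitted separately by cohort to log clearance from both days. It "will include fixed effects for route (oral or iv) and for day (1 and 14) and a random effect for subject".

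**The concern.** The unit of exclusion is the subject, and there is only one PK set. Nothing in SAP 10.2 says that a Period 2 problem affects Period 2 results only. Protocol 4.1.2 also has criteria that can first be met after the Day 10 sample. Criterion 21 covers a "Positive urine alcohol test or urine drug screen at screening or each admission (Day -1 of each period"), and criterion 2 repeats the pregnancy test at the same admissions. Day -1 of Period 2 is Day 14 of Period 1. Protocol 5.1.2.1 foresees dosing interruptions and says that "temporary interruptions will have to be very limited in order to not jeopardize" the PK objectives.

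On a literal reading, a subject with a full single-dose oral and IV profile could leave the primary analysis because of something that happened afterwards. That does not fit SAP 6.1. With 8 subjects per cohort, each avoidable loss widens the interval for F.

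**Working it through.** **Does the text prescribe the loss?**

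- *Readmission screen.* Protocol 4.1.2 criteria bar entry to the study, and protocol 9.2 forbids eligibility waivers. A subject who tests positive at readmission and is not dosed has been handled as the criterion intends. That is not plainly a significant violation of it.
- *Interruption.* Protocol 5.1.2.1 allows limited interruptions after discussion with the Medical Monitor. A permitted interruption is not in itself a deviation, still less a significant one.
- *Incomplete data.* This can be read as incomplete for the analysis in hand. Day 1 F needs only the Period 1 oral and IV areas.
- *Other text.* Protocol 4.1 counts subjects giving data from the single-dose or multiple-dose parts. SAP 9.2.2 makes single and repeated dosing separate treatments (A and B, C and D). SAP 16.2.2 summarises parameters by treatment, day and analyte with the number of subjects, and applies its R² and extrapolation rules to parameters.

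**What would a loss cost?** Inputs from protocol 6.1 and SAP 6.1: 8 enrolled per cohort, target at least 6, variability 35%, 90% interval, stated factor 1.50 with 6 subjects.

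*Plan's own figure.* For a paired comparison on one day, with the stated variability taken as the log-scale SD:

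factor = exp( t(0.95, n−1) × s × √(2/n) )

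For n = 6 and s = 0.35: exp(2.015 × 0.2021) = 1.503. With s = 0.30 and 0.40 it gives 1.418 and 1.593. These match protocol Table 4 (1.42, 1.50, 1.59).

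*Single-day basis, s = 0.35:*

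| Subjects kept | t | 0.35 × √(2/n) | Factor |
|---|---|---|---|
| 8 | 1.895 | 0.1750 | 1.39 |
| 7 | 1.943 | 0.1871 | 1.44 |
| 6 | 2.015 | 0.2021 | 1.50 |
| 5 | 2.132 | 0.2214 | 1.60 |

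The stated 1.50 is missed only if three or more of 8 are removed and not replaced.

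*Planned two-day model.* Each subject-day gives one oral and one IV clearance. Let P be the number of such pairs. Residual df = observations − subjects − 2, and

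factor = exp( t(0.95, df) × 0.35 × √(2/P) )

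With 8 complete subjects, P = 16, df = 32 − 8 − 2 = 22, and the factor is 1.237. For subjects who stop in Period 2:

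| Period 2 stops | Day 1 kept: P, df | Factor | Subject dropped: P, df | Factor |
|---|---|---|---|---|
| 1 | 15, 20 | 1.247 | 14, 19 | 1.257 |
| 2 | 14, 18 | 1.258 | 12, 16 | 1.283 |
| 3 | 13, 16 | 1.271 | 10, 13 | 1.319 |

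With whole subjects dropped, the factor is 1.373 for 4 complete subjects (P = 8, df = 10) and 1.466 for 3 (P = 6, df = 7). It passes 1.50 only with 2 left (P = 4, df = 4: exp(2.132 × 0.2475) = 1.69).

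The documents give no exclusion rate, so the check is conditional on the number lost and attaches no probability to it.

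**The case for a change.** The best case for a change is that a primary analysis set should not depend on goodwill. Reading *incomplete* narrowly does not settle the violation and deviation grounds. The study is open-label, and a decision made before database closure is not necessarily made before concentrations are known. SAP 6.1 is a sample-size statement and does not govern the analysis set. Replacement is discretionary, and it restores the count without restoring the data set aside. The mixed model can use a subject with Day 1 data only, so nothing in the analysis requires whole-subject removal. The remedy would be a few sentences, with no protocol amendment, since "This SAP supersedes the statistical considerations identified in the protocol; where considerations are substantially different, they will be so identified".

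Much of this stands. SAP 10.2 is by subject and silent on period, it sits awkwardly beside SAP 6.1, and clearer wording would cost little. What does not stand is the step from silence to harm. Neither cited Period 2 trigger is shown to be a significant violation or deviation, and decisions must be documented with reasons.

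A by-period rule would also need care at the very example that prompts it. Day -1 of Period 2 is also Day 14 of Period 1, so a positive screen that day could be assigned to either. A Period 1 ineligibility discovered later should still count against Period 1 results.

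**Conclusion.** No change is called for. SAP 10.2 leaves the scope of its exclusions unstated. The surrounding text shows how an analyst would fill the gap: keep the single-dose results of a subject with a valid Period 1 profile, and treat Day 14 results on their own merits.

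If the literal reading were applied, the harm would be a modest loss of precision. In the planned model the factor is 1.25 with Day 1 data kept against 1.26 with the subject dropped for one Period 2 loss, 1.26 against 1.28 for two, and 1.27 against 1.32 for three. On the single-day basis used for sample size, the stated 1.50 is still met with 6 subjects, and replacement or further enrolment is permitted. No bias in F is shown.

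These figures assume the plan's 35% as the log-scale within-subject SD, the same on both days, and no further variance component in the two-day model. A Day 1-only estimate follows the single-day column, where the losses cost more. A clarifying sentence would be a harmless courtesy, but the conclusions of the trial do not depend on it.

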## 11.0 Subject Disposition

The number and percentage of subjects randomized, dosed, and members of each analysis set will be presented. The number and percentage of subjects who withdrew from the study prematurely and a breakdown of the corresponding reasons for withdrawal will also be presented. If the reason for discontinuation is "other", further specifications will only be listed.

## 12.0 Protocol Deviations and Violations

Protocol deviations/violations will be included in the CSR.

## 13.0 Demographic and Baseline Characteristics

### 13.1 Demographics

All demographic data as collected during the screening visit will be listed by subject. Genotype information will be included.

Subject demographics will be summarized descriptively for all subjects by genotype and overall. The summary will include the subjects' age (in years), gender, race, ethnicity, weight (in kg), height (in cm), and body mass index (BMI) (in kg/m^2) at baseline. Demographics will be summarized for the safety and (if necessary) for the PK sets.

## 13.2 Medical History

Medical history will be listed including the coding according to the Medical Dictionary for Regulatory Activities (MedDRA; latest version).

## 13.3 Other Baseline Characteristics

- Drug and alcohol screen: The results of urine drug screen (barbiturates, benzodiazepines, methadone, amphetamines [including ecstasy], methamphetamines, opiates, cocaine, and cannabinoids and urine alcohol test will be listed.
- Serology: The results of serology (human immunodeficiency virus (HIV)-1 and HIV-2, hepatitis B virus surface antigen (HBsAg), hepatitis C virus (HCV) antibody) at screening will be listed.
- Pregnancy test (females only): Serum pregnancy test results (beta-human chorionic gonadotropin) and follicle-stimulating hormone (FSH) test results will be listed for each female subject at screening. All other timepoints for serum pregnancy test will be listed as well.
- Non-compliance to inclusion or exclusion criteria (if any) will be listed.

## 14.0 Concomitant Medications

Concomitant medications, categorized by medication group and subgroup according to GNE Drug dictionary, will be summarized. The number and percentage of subjects using each medication will be displayed with the number and percentage of subjects using at least one medication within each medication group and subgroup, by treatment.

Concomitant medication will be listed. Medications with an end date prior to the first dose of study drug will be considered prior medications and will be noted in the listing. If a partial date allows a medication to be considered concomitant it will be categorized as such.

## 15.0 Treatment Compliance and Exposure

Exposure data will be listed by subject.

The number of subjects receiving each dose of study drug will be summarized.

## 16.0 Pharmacokinetic Analyses

PK concentrations will be collected in plasma.

### 16.1 Pharmacokinetic Variables

#### 16.1.1 Concentrations

- Plasma concentration of balovaptan
- Plasma concentration of [C]-balovaptan
- Plasma concentration of metabolites (M2, M3)
- [REDACTED]
- [REDACTED]

#### 16.1.2 Parameters

- PK Parameters for balovaptan, [C]-balovaptan, M2 and M3 as defined in [Table 1](#) and [Table 2](#).

**Table 1: Plasma Parameters**

Parameter	Description	Analyte/Analysis Period	SAS Programming Notes
C max	Maximum plasma concentration. Observed peak analyte concentration obtained directly from the experimental data without interpolation, expressed in concentration units	All analytes	C max from WNL
C trough	Concentration at the end of the dosing interval (tau)	All analytes/ Period 2	The concentration at 24 h calculated in SAS
C last	Last measurable plasma concentration	All analytes	Calculated in SAS
t max	Time to maximum plasma concentration. First observed time to reach peak analyte concentration obtained directly from the experimental data without interpolation, expressed in time units.	All analytes	T max from WNL
AUC 0-last	Area under the concentration-time curve (time 0 to time of last quantifiable concentration).	All analytes/ Period 1	AUC last from WNL
AUC 0-inf	Area under the serum concentration-time curve (time 0 to infinity). Percent extrapolation less than or equal to 20% is required to obtain a reliable AUC inf .	All analytes/ Period 1	AUC INF_obs from WNL If AUC_%Extrap_obs >20% then parameter is not included
AUC 0-24h	Area under the serum concentration-time curve from time 0 to 24 hours post-dose	All analytes/ Period 1 and 2	AUC 0-24 from WNL where partial time =24, if missing for a subject then AUC at nominal time 24 hr from summary file is used for AUC 0-24
λ z	Terminal phase rate constant calculated by linear regression of the terminal log-linear portion of the concentration vs. time curve. Linear regression of at least three points and an adjusted R  greater than 0.70 are required to obtain a reliable λ z .	All analytes	Lambda_z from WNL If adjusted R  ≤ 0.7 the parameter is not estimated
t 1/2	Terminal phase half-life expressed in time units. Percent extrapolation <20% and adjusted R  greater than 0.7 is required to obtain a reliable t 1/2 .	All analytes	HL_Lambda_z from WNL If adjusted R  ≤ 0.7 the parameter is not estimated
t last	Time of last measurable plasma concentration	All analytes	Determined in SAS
R AUC	Accumulation ratio for AUC 0-24h	All analytes	Day 14 AUC 0-24h Period 2/ Day 1 AUC 0-24h Period 1 Calculated in SAS

R Cmax	Accumulation ratio for C max	All analytes	Day 14 C max Period 2/ Day 1 C max Period 1 Calculated in SAS
R Ctrough	Accumulation ratio for C trough	All analytes	Day 14 C trough Period 2/ Day 1 C trough Period 1 (24 h sample on Day 2) Calculated in SAS
F	Absolute bioavailability (oral versus IV in %)	Balovaptan ([  C]- balovaptan)	Calculated in SAS as $F = \frac{AUC_{oral+DIV}}{AUC_{IV+Doral}} * 100$ AUC 0-inf of Balovaptan as AUC oral and AUC 0-inf of [  C]-Balovaptan as AUC IV
CL	Total body clearance (IV administration only) obtained by dividing the total dose of parent drug by its corresponding AUC 0-inf	[  C]-balovaptan	CL_obs from WNL
CL/f	Apparent total plasma clearance of drug after oral administration obtained by dividing the total dose of parent drug by its corresponding AUC 0-inf	balovaptan	CL_F_obs from WNL
V ss	Volume of distribution at steady state (IV administration only)	[  C]-balovaptan	V ss_obs from WNL

Note: AUCs will be calculated using linear up / log down, expressed in units of concentration x time.

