#### 5.2 Secondary Objectives

- To determine the absolute oral bioavailability of a single dose of 50 mg balovaptan.
- To determine the absolute oral bioavailability of balovaptan after once daily doses of 10 mg or 50 mg for 14 days.
- To characterize the dose- and time-dependency of the PK of oral balovaptan.
- To determine plasma concentrations of [C]-labeled balovaptan, balovaptan, and its metabolites M2, and M3, following a single oral dose of balovaptan 10 mg or 50 mg together with a slow intravenous (IV) infusion of a microdose of [C]-labeled balovaptan.
- To determine plasma concentrations of [C]-labeled balovaptan, balovaptan, and its metabolites M2, and M3, following once daily oral dosing of 10 mg or 50 mg once daily (QD) for 14 days together with a slow IV infusion of a microdose of [C]-labeled balovaptan after the last oral dose.
- To evaluate the safety and tolerability of balovaptan 10 mg QD and 50 mg QD.

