##### 5.2.1 Secondary Endpoints

- Absolute bioavailability (F) for balovaptan at the indicated dose level.

- Plasma concentrations and associated PK parameters for [C]-labeled balovaptan, balovaptan, and its metabolites M2, and M3, including but not limited to  $C_{max}$ ,  $t_{max}$ ,  $t_{1/2}$ ,  $AUC_{last}$ ,  $AUC_{inf}$ ,  $AUC_{0-24}$ ,  $C_{last}$ ,  $t_{last}$ ,  $\lambda_z$ , and (for [C]-parent only) CL on Day 1 and Day 14 and  $V_{ss}$  on Day 1 and Day 14.  
Any other parameter as appropriate (see Table 1)
- Adverse events (AEs), clinical laboratory values, vital signs, electrocardiogram (ECG), and physical examination.

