#### 9.1.2 Imputation

Except for the substitution of any PK concentrations below the lower limit of quantification (LLOQ) (see [Section 16.2](#)) and missing start or end date/times of AEs for the calculation of onset and duration (see [Section 17.1.1](#)), any missing data will not be imputed.

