## Appendix 4: List of End of Text Outputs

List of End of Text Tables and Figures:		
Output	Title	Population Set
Section 14.1 – Disposition and Demographic Data		
Table 14.1.1	Summary of Subject Disposition	Safety
Table 14.1.2.1	Summary of Demographics	Safety
Table 14.1.2.2	Summary of Demographics (if applicable)	PK
Section 14.2 – Pharmacokinetic Data		
Table 14.2.1	Individual Values and Descriptive Statistics of Balovaptan and [  C]-Balovaptan Plasma Concentrations by Treatment, Analysis Day and Time-Point	PK
Table 14.2.2	Individual Values and Descriptive Statistics of Balovaptan and [  C]-Balovaptan Plasma PK Parameters by Treatment and Analysis Day	PK
Table 14.2.3	Individual Values and Descriptive Statistics of Balovaptan Metabolite (M2 and M3) Plasma Concentrations by Treatment, Analysis Day and Time-Point	PK
Table 14.2.4	Individual Values and Descriptive Statistics of Balovaptan Metabolite (M2 and M3) Plasma PK Parameters by Treatment and Analysis Day	PK
Table 14.2.5	Individual Values of Balovaptan and Balovaptan Metabolite (M2 and M3) Concentrations by Treatment, Analysis Day and Time-Point	PK
Table 14.2.6	Individual Values of Balovaptan and Balovaptan Metabolite (M2 and M3) Ratios	PK
Table 14.2.7	Ratio of geometric means of microdose IV kinetics (clearance) with that of oral dose	PK
Figure 14.2.8.1	Geometric Mean Balovaptan Plasma Concentrations versus Time (Linear and Semi-Logarithmic Scale) by Treatment and Analysis Day	PK
Figure 14.2.8.2	Geometric Mean [  C]-Balovaptan Plasma Concentrations versus Time (Linear and Semi-Logarithmic Scale) by Treatment and Analysis Day	PK
Figure 14.2.8.3	Geometric Mean Balovaptan Metabolite (M2 and M3) Plasma Concentrations versus Time (Linear and Semi-Logarithmic Scale) by Treatment and Analysis Day	PK
Figure 14.2.8.4	Geometric Mean Balovaptan and Balovaptan Metabolite (M2 and M3) Plasma Trough Concentrations (Linear and Semi-Logarithmic Scale) by Treatment	PK
Figure 14.2.9.1	Combined Individual Balovaptan Plasma Concentrations versus Time (Linear and Semi-Logarithmic Scale)	PK

Figure 14.2.9.2	Combined Individual [  C]-Balovaptan Plasma Concentrations versus Time (Linear and Semi-Logarithmic Scale)	PK
Figure 14.2.9.3	Combined Individual Balovaptan Metabolite (M2 and M3) Plasma Concentrations versus Time (Linear and Semi-Logarithmic Scale)	PK

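### Day 14 F and CL/F are computed from an oral AUC0-inf that still contains 13 earlier doses; the steady-state AUC0-24 should be used instead

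*SAP*

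**What the plan says.** **F and clearance.** SAP Table 1 defines F as the dose-normalised AUC0-inf of oral balovaptan over that of the [13C] tracer. It defines CL and CL/F as dose over AUC0-inf. None of these rows names a period. The AUC0-inf row itself is limited to Period 1. AUC0-24 is listed for both periods. Protocol 6.6 ties AUCinf to a single dose and AUC0-24 to the dosing interval at steady state.

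**What is needed on Day 14.** One secondary objective in SAP 5.2 is F "after once daily doses of 10 mg or 50 mg for 14 days". The endpoints in SAP 5.2.1 include tracer "CL on Day 1 and Day 14".

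**The model.** SAP 16.2.2 fits, per cohort, a mixed model to "natural logarithm transformed clearance (CL and CL/F"), with fixed effects for route and day and a random subject effect. There is no route-by-day term, so each cohort yields one ratio pooled over Days 1 and 14. It is reported as "Ratio of geometric means of microdose IV kinetics (clearance) with that of oral dose" (Table 14.2.7).

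**The extrapolation cut.** The AUC0-inf row of Table 1 says "If AUC_%Extrap_obs >20% then parameter is not included". SAP 16.2.2 says that parameters above 20% "will be flagged and excluded from descriptive statistics".

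**The concern.** Dose over AUC0-inf gives a clearance only if the area comes from that dose alone. This is true of the tracer on both days and of the oral dose on Day 1. It is not true of the oral dose on Day 14, because the plasma then also carries what remains of 13 earlier daily doses. All of that extra area is credited to the last dose, so Day 14 CL/F comes out too low and Day 14 F too high.

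Three results are at stake. Day 14 F, a secondary objective, would be wrong by a multiple. Comparing Day 1 with Day 14 would show an apparent rise in F over time even if F were constant, and time-dependency is itself a secondary objective. The pooled ratio, the only estimate for which the SAP plans a confidence interval, would inherit part of the error.

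**Working it through.** **1. The plan's own figure.** Protocol 6.1 and SAP 6.1 give a 90% CI factor of 1.50 for the CL versus CL/F ratio (6 subjects, 35% variability). It reproduces: exp(t(0.95; 5 df) × 0.35 × √(2/6)) = exp(2.015 × 0.35 × 0.577) = 1.50. The same formula gives 1.42 at 30% and 1.59 at 40%, matching protocol Table 4. The figure is not in dispute. It serves below as a yardstick.

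**2. Residue in the Day 14 oral AUC0-inf.** Inputs: half-life about 46 h after the Day 14 dose (protocol 1.2.1.1), a 24 h interval and 14 doses. Assume one-compartment decay. Each earlier dose adds a tail that shrinks by q = 2^(−24/46) = 0.697 per day.
- Day 14 AUC0-inf over the area due to one dose = (1 − q^14)/(1 − q) = 0.9937/0.3035 = **3.27** (3.30 at full steady state).
- From reported accumulation (about 4-fold after 12 mg, 2-fold after 52 mg): under stationary one-compartment kinetics the accumulation ratio is 1/(1 − q), the same quantity. The range is therefore **about 2 to 4**.
- If 30% of each dose's area lay in a distribution phase over within 24 h (assumed), the factor at 46 h would be 1 + 0.7 × 2.27 = 2.6, inside that range.

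**3. Effect on Day 14 F.** F is proportional to the oral area, so it is overstated by the same factor. At 3.27, any true F above 100/3.27 = 31% would be reported as more than 100%.

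**4. Effect on the pooled ratio.** With complete data the route effect is the average of the two days' log ratios. Day 1 is right and Day 14 is off by ln 3.27, so the pooled log ratio is off by half of that: √3.27 = **1.81**. Over 2 to 4 the shift is √2 = 1.4 to √4 = 2. At 46 h the shift exceeds the 1.50 factor in step 1.

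**5. Does AUC0-24 solve it?** At steady state the area over one interval equals the area due to one dose. After 14 doses the shortfall is q^14: 0.6% at 46 h, and 0.75^14 = 1.8% for 4-fold accumulation. The tracer needs no such correction. Its two doses are 27 days (648 h) apart, about 14 half-lives at 46 h.

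**6. The 20% cut (minor).** The last tracer sample is 108 − 1.25 − 0.25 = 106.5 h after the infusion ends (protocol Appendix 2, SAP Appendix 3). If a share f of the area lies in a distribution phase, the extrapolated fraction is (1 − f) × 2^(−106.5/half-life). It passes 20% at half-lives of 45.9, 49.1, 53.2 and 58.9 h for f = 0, 0.1, 0.2 and 0.3. Taking half-life as lognormal with mean 46 h and CV 20–40% (assumed), the share of subjects failing on Day 14 is:

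| f (assumed) | Share failing |
|---|---|
| 0 | 43–47% |
| 0.1 | 34–36% |
| 0.2 | 20–28% |
| 0.3 | 9–20% |

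**The case against.** **The Period 1 limit.** Since Table 1 lists AUC0-inf for Period 1 only, one can argue that no Day 14 oral AUC0-inf was intended and that the pharmacokineticist would turn to AUC0-24. That may well happen, and an F far above 100% would raise the alarm. But no text says so. The F and CL/F definitions name AUC0-inf and nothing else, and the model calls for Day 14 values. Read strictly, the Period 1 limit leaves Day 14 F and tracer CL without an input. Either way Table 1 needs changing.

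**The size.** The 46 h figure is an approximate oral mean from earlier dosing, and the decay model is simple. The protocol calls the kinetics time-dependent, so the reported accumulation may partly reflect changing clearance. This is why a range is given. At any point in the range the error is a multiple, not a few percent.

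**Stronger readings that the documents do not support.** A reader might infer that Table 1 and SAP 16.2.2 contradict each other on the 20% cut, one deleting a value that the other keeps. But "If AUC_%Extrap_obs >20% then parameter is not included" does not say what the parameter is left out of, and can mean the summaries, which agrees with 16.2.2. On that reading F is not lost, and the statement in SAP 9.1.2 that "any missing data will not be imputed" does not come into play. A reader might also infer that the fate of flagged values in the model is open. SAP 9.1.5 names statistical analysis separately when it excludes unscheduled measurements from both, whereas 16.2.2 names descriptive statistics only. The natural reading is that flagged clearances stay in the model. Finally, a reader might infer that the cut thins out the primary Day 1 analysis. No Day 1 half-life is stated, so that is not shown.

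**Conclusion.** The concern holds for Day 14. As written, the oral F and CL/F there rest on an area that includes 13 earlier doses. Day 14 F would be overstated about 3.3-fold at a 46 h half-life, or about 2- to 4-fold by the reported accumulation. The pooled CL to CL/F ratio would be overstated about 1.8-fold (1.4- to 2-fold over the range). These sizes assume one-compartment superposition, complete data on both days and AUC0-inf used on Day 14 as Table 1 defines it. Day 1 F values, which are the primary endpoint, carry no residue. The pooled ratio in Table 14.2.7 should not be taken for the single-dose F while Day 14 is computed this way.

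The 20% cut is a point of wording. It could remove about 9–47% of subjects from the Day 14 tracer CL summaries. That range depends on an assumed spread of half-lives and an assumed distribution share, and on the tracer sharing the oral half-life.

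**What to change.** 1. In SAP Table 1, define Day 14 oral CL/F as dose over steady-state AUC0-24. Define Day 14 F as dose-normalised oral AUC0-24 over dose-normalised tracer AUC0-inf. Keep the AUC0-inf definitions for Day 1, and use these Day 14 values in the 16.2.2 model.
2. List the tracer's AUC0-inf for Period 2 in Table 1.
3. Minor: use the same wording for the 20% cut in Table 1 and 16.2.2, and confirm that flagged CL and CL/F values stay in the model. Give the number of subject-days in Table 14.2.7. Add a sensitivity analysis restricted to extrapolation of at most 20%, dropping CL and CL/F together for a failing subject-day so that the ratio stays paired.

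The cost is SAP wording, changed programming notes and one sensitivity table, with no new samples or assays. The new Day 14 definitions rely on steady state. That can be checked on the predose samples of Days 12, 13 and 14, and the expected shortfall is under 2%. Flagged clearances kept in the model carry more extrapolation error, which the sensitivity analysis would show.
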